Although evidence suggests that exercise can improve mobility and perhaps decrease the rate and extent of disability (i.e. impaired function) in people with MS, most studies related to exercise have failed to screen for people with walking problems using objective assessment.²¹⁻³⁸ Evidence does show, however, that traditional, facility-based exercise training, particularly in a setting where other people with MS are exercising or under the supervision of exercise personnel, may help people with MS consistently participate in exercise or to exercise at a higher, more intense level. Despite this evidence, lack of access to these programs may make it difficult to engage in a GEMS-S program.³⁹⁻⁴³ Telerehabilitation (telerehab) has great potential to overcome challenges associated with facility-based programs. Telerehab can include videoconferencing, remote monitoring of signs and activity, and dissemination of specialized and individualized information via electronic mechanisms. Both facility-based and telerehab exercise training have yielded positive results in people with MS,²¹⁻³⁸ but have not been compared head-to-head. The current study will fill this gap in the evidence base and compare the outcomes of delivering the same exercise interventions in a facility (facility-based exercise training or GEMS-S) or in the home/community using a telerehab approach (telerehab delivered exercise training or GEMS-T). The interventions are designed to be identical in content, with the only difference being the mode of training delivery.

This study will yield important data to inform people with MS who have objective walking impairment, as well as healthcare providers, exercise trainers, payers, and policy makers, about exercise options for people with MS. Our **main hypothesis** is that there will be no difference in outcomes when the evidence-based individualized exercise program is delivered in a facility (GEMS-S) or via telerehab (GEMS-T) (i.e., walking and other outcomes will improve similarly between conditions). Our null hypothesis is that GEMS-T is inferior to GEMS-S. A secondary hypothesis is that patients who perform their preferred **choice** of program (GEMS-T(Choice) or GEMS-S(Choice)) will have better outcomes in self-efficacy, adherence, and adoption of exercise than no choice conditions.

SPECIFIC AIMS

Our specific aims (SAs) are as follows:

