To evaluate and compare the effectiveness between participants randomized to their preferred delivery mode (GEMS-T [Choice] or GEMS-S [Choice]) with those who are not randomized to their preferred delivery mode, we will use the same analysis model but examine an interaction term for choice and treatment. We will assess if the effect of Choice is the same for both treatments. Logistic regression will be used to assess the interaction between choice and adherence and attendance or dropouts. We also will examine time to dropout and/or time until dropout or poor compliance (which will be defined prior to final analyses). We also are interested in examining the intensity or compliance of the intervention to the choice as well as impact on the primary endpoint as noted above.

We will also utilize mediation analyses to understand if the changes induced by exercise are mediated via the changes in self-efficacy. Here we will use the approach by MacKinnon built on Judd and Kenny.⁴⁵⁻⁵¹ The MSWS-12, MFIS-21 and Neuro-QOL will all be analyzed using regression models similar to the timed walk models above and will utilize the same contrasts for examining choice as well as treatment effects.

DATA MANAGEMENT

The Data Management Center (DMC) will be housed at the Accelerated Cure Project/iConquerMS led by project co-investigator, [name]. The DMC will collaborate and communicate with the Steering Committee and Advisory Board as outlined in Table 4.

Table 4. Responsibilities/Tasks of Data Management Center (iConquerMS/[name])
Review the proposed trial protocol and contribute to finalizing that document
Develop electronic and paper case report forms for data collection
Develop Standard Operating Procedures and a study Manual of Procedures
Develop and maintain an electronic data management system that will include a web-based data entry system and project website for the study
Create, distribute and oversee data entry processes for all sites
Train and certify users from each site in the data entry
Receive, collect, process, store provide quality control and assist in data analysis of data collected from the participating clinical sites and central reading centers
Prepare and distribute periodic technical and statistical reports to the Steering Committee, participating sites, committees (including the DSMB) and the PCORI office, as appropriate

Data safety and adequacy

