SA2: Evaluate and compare the effectiveness between participants randomized to their preferred delivery mode (TET(Choice) or FET (Choice)) and those who are not randomized to their preferred delivery mode (TET or FET). For this aim we will use the same models as the primary but examining and interaction term for Choice and treatment and contrasts will be conducted comparing the four cells. We will assess if the effect of Choice is the same for both treatments. Logistic regression will be used to assess the interaction between choice and adherence and attendance or dropouts. We also will examine time to dropout and/or time until dropout or poor compliance (which will be defined prior to final analyses). We also are interested in examining the intensity or compliance of the intervention to the choice as well as impact on the primary endpoint as noted above.

SA3: Evaluate changes in self-efficacy and adoption of exercise between these groups (TET, FET, TET(Choice), FET(Choice)). Self-efficacy and adoption of exercise are discussed above and use the same models and approach. We will also utilize mediation analyses to understand if the changes induced by exercise are mediated via the changes in self-efficacy. Here we will use the approach by MacKinnon built on Judd and Kenny.⁷⁹⁻⁸⁴ Analyses of the MSWS-12, MFIS, and the NeuroQOL will all be analyzed using regression models similar to the timed walk models above and will utilize the same contrasts for examining choice as well as treatment effects.

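### SA2 and SA3 name no randomised contrast for the hypothesis that choice helps: the interaction asks a different question, and within-mode cell comparisons mix choice with self-selection

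*SAP*

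**What the plan says.** The secondary hypothesis (Protocol, Background and Significance) is directional: participants in their chosen programme "will have better outcomes in self-efficacy, adherence, and adoption of exercise than no choice conditions". The SAP's section on the goals of the HTE analyses counts the effect of choice among the study's primary interests.

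For SA2 the Protocol's Data analysis plan says "we will use the same analysis model but examine an interaction term for choice and treatment". The SAP uses the "same models as the primary but examining and interaction term for Choice and treatment and contrasts will be conducted comparing the four cells", and states the purpose: "We will assess if the effect of Choice is the same for both treatments". For the behavioural outcomes it adds "Logistic regression will be used to assess the interaction between choice and adherence and attendance or dropouts" and "We also will examine time to dropout and/or time until dropout or poor compliance". SA3 says that the MSWS-12, MFIS and NeuroQOL analyses "will utilize the same contrasts for examining choice as well as treatment effects". No coefficients are given for any of these contrasts.

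The Protocol's Participants section randomises 200 people to Choice and 200 to No Choice, and the latter 100:100 to the two modes. Its Intervention section counts 200 people per mode. The SAP calls the modes TET (telerehab, GEMS-T) and FET (facility, GEMS-S). Its SA2 comparator is "those who are not randomized to their preferred delivery mode (TET or FET"), which means the two No Choice cells.

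**The concern.** Randomisation protects one comparison that bears on choice: the Choice arm against the No Choice arm. SA2 and SA3 do not name it.

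- **Interaction.** It compares the choice effect in telerehab with the choice effect in the facility. A benefit of equal size in both modes cancels out. A prognostic difference between people who prefer telerehab and people who prefer the facility does not cancel.
- **Cell comparisons.** TET(Choice) contains only people who wanted telerehab, while TET contains both kinds of people. The same holds for FET(Choice) and FET. Each pair mixes the effect of choice with self-selection.

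If the analysis follows the terms that are named, a real benefit could be missed or mis-sized, and self-selection could be reported as an effect of choice. Choice is a secondary hypothesis, but it is the reason for the two-stage design.

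**Working it through.** There is no figure to reproduce: neither document gives an alpha, SD, effect size or power for the choice question.

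**Inputs from the documents.** 200 Choice; 100 + 100 No Choice; 200 per mode in total. Then 200 − 100 = 100 choosers per mode, an implied 50:50 uptake, although participants decide it.

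**Assumptions.** SD 1; two-sided 5%; p = share preferring telerehab; s = gap between preference groups left after the planned covariates; a, b = gain from being matched to telerehab or facility; c = gain from choosing itself; t = mode effect.

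**Cell means**
- TET(Choice) = s + t + a + c
- FET(Choice) = b + c
- TET = p(s + a) + t
- FET = ps + (1 − p)b

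**What each contrast estimates**

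| Contrast | Expectation |
|---|---|
| Interaction | s + (1 − p)a − pb |
| TET(Choice) − TET | (1 − p)(s + a) + c |
| FET(Choice) − FET | p(b − s) + c |
| Equal weights on the two pairs | 0.5[(1 − p)a + pb + (1 − 2p)s] + c |
| Uptake weights | p(1 − p)(a + b) + c |
| Choice arm − No Choice arm | 0.5[pa + (1 − p)b] + c + (p − 0.5)t |

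The interaction contains no c. Only the last two rows are free of s at every split.

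**Selection only (a = b = c = 0), p = 0.5, s = 0.4.** No Choice cells mix both preference groups, so their variance is 1 + 0.25 × 0.16 = 1.04.
- Interaction: 0.4; SE √[(1 + 1 + 1.04 + 1.04)/100] = 0.202; ratio 1.98; rejects about 50%.
- TET(Choice) − TET: 0.5 × 0.4 = 0.2; SE √(2.04/100) = 0.143; ratio 1.40; rejects about 29%.
- Uptake-weighted and arm contrasts: 0; reject 5%.

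For s = 0.1/0.2/0.3/0.4, simulation (20,000 replicates per setting) gives 8/17/32/50% for the interaction and 7/11/19/29% for the single cell.

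**Uniform benefit (c = 0.3, s = 0), p = 0.5.** The interaction estimates 0 and rejects 5%. A randomised contrast estimates 0.3 with SE 0.1, so power is about 85%. If s = +0.4 or −0.4 is present as well, TET(Choice) − TET reads 0.3 ± 0.2, that is 0.50 or 0.10.

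**Uneven uptake, p = 0.7**
- Selection only, s = 0.4: equal weights give 0.5 × (−0.4) × 0.4 = −0.08 and reject about 11%. With s = 0.2 they reject 6.8%.
- Matching only, a = b = 0.6: uptake weights give 0.21 × 1.2 = 0.252 (power 66%); the arm difference gives 0.5 × 0.6 = 0.30 (power about 83%).
- Mode effect only, t = 0.2: uptake weights give 0; the arm difference gives 0.2 × 0.2 = 0.04.

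**Adherence.** Take no choice effect, chooser adherence expit(1 + S) in telerehab and expit(1) in facility, and p = 0.7. For S = 1, each No Choice cell has risk 0.7 × 0.881 + 0.3 × 0.731 = 0.836, with log-odds 1.63. Uptake-weighting the choosers' log-odds gives 0.7 × 2 + 0.3 × 1 = 1.70, a spurious 0.07. For S = 0.5/1.0/1.5 it is 0.02/0.07/0.18. On the risk scale it is 0.

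**The case against.** The strongest reply is that the plan does analyse choice. SA2 and SA3 both announce contrasts, and a model with a Choice × treatment term normally carries a choice main effect. At the only split that the documents imply, 50:50, equal weights, uptake weights and the arm difference all have the same expectation. At 70:30 the penalty for equal weights is modest. The SA2 models also inherit adjustment for site, age, gender and baseline EDSS, so a residual gap of 0.4 SD may be too large. The phrase about choice interacting with adherence is most naturally loose wording for an association.

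Much of this stands. A reader might infer that no test of choice is planned, or that no scale is given. The documents do not support either: contrasts are planned, and linear and logistic models are named. The missing weights are also a small matter near 50:50.

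What remains is that none of the planned contrasts is tied to the randomisation. The meaning of a main effect depends on coding that is not stated. The single-cell comparisons carry selection at any split, 50:50 included.

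On labelling, SA2 describes No Choice participants as not randomised to their preferred mode, although under 1:1 allocation about half would receive it by chance if everyone has a preference. The parenthesis identifies the cells, so this is editorial.

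**Conclusion.** The point holds and should be fixed. The one outcome-model term named for SA2 does not test the stated choice hypothesis, and the natural four-cell comparisons are not randomised comparisons. That follows from the text and the cell algebra, whatever the effect sizes. The rejection rates (about 50% and 29% under selection alone, 5% for the interaction under a uniform 0.3 SD benefit) rest on assumed gaps and SD 1. They show the direction and possible scale of the problem, not a forecast.

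A separate, secondary point concerns SA1. The SAP does not say whether the 200 Choice participants enter the mode comparison. The count of 200 per mode suggests pooling, while SA2 uses bare TET and FET for the No Choice cells. A reader might infer that the non-inferiority estimate is confounded by self-selection, but the documents do not establish that, because pooling is never stated. If all 400 were pooled at 50:50 uptake, telerehab-preferring people would make up 150/200 of one group and 50/200 of the other, so the bias would be 0.5 times the residual preference-group gap.

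The SAP's Sensitivity analyses section also adjusts for preference at entry. The Protocol's study measures list no such item for No Choice participants; the Choice form is for the Choice group.

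**What to change.** In SAP SA2 and SA3, name one contrast protected by the first-stage randomisation as the test of the choice hypothesis, and fix its weights in advance. The sponsor picks one and may report the other.

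- **Option 1:** Choice-arm mean − [q × TET + (1 − q) × FET]. TET and FET are the No Choice cells, q is the observed share of the Choice arm choosing telerehab, and the SE treats q as estimated (delta method or bootstrap). It is free of selection and of the mode effect.
- **Option 2:** Choice arm − No Choice arm, 200 versus 200. It is free of selection and more powerful at uneven uptake if benefit comes from matching, but it picks up any mode effect when uptake is uneven.

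For adherence and dropout, work on the risk scale: Choice-arm risk − [q × TET risk + (1 − q) × FET risk] under option 1. For time to dropout, use Kaplan-Meier risks at a stated time or restricted mean times in the same way.

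Keep the interaction as a separate question and state that it includes self-selection. Label any contrast that uses a single chooser cell as non-randomised.

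For SA1, state the analysis set; if Choice participants are pooled, report the randomised 100 versus 100 contrast beside the pooled estimate. Identify where preference is recorded for No Choice participants, or drop that adjustment.

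The cost is SAP wording and a few lines of code, with no new data. The downside of option 1 is lost power at uneven uptake: 66% against about 83% in the 70:30 matching example.

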4. Able to travel to a GEMS-S site for testing and training
5. Accessible, technological platform for GEMS-T (i.e. computer or DVD player and TV,

and telephone)

6. A score of between 25 and 75 on the MSWS-12
7. Timed 25-foot walk test (T25FWT) time of between 6 seconds and 3 minutes
8. Medically stable or approval from physician to participate in exercise studies
9. A score of between 3 and 6 (inclusive) on the Patient Determined Disability Steps

Exclusion criteria:

1. Documented MS relapse in the past 30 days
2. Have had falls in the past three months that the study investigator determines makes participation unsafe
3. Unable to walk 25 feet
4. Already exercises at recommended levels as determined by a score of 25 or higher on the Godin Leisure-Time Exercise questionnaire
5. Has other neurological (e.g., stroke) or musculoskeletal conditions or other co-morbidities
6. Has cognitive difficulties as determined by a Mini Mental Status Exam score <19
7. Is not proficient in English
8. Is physically unable to complete the second T25FWT trial
9. Any other concern that the investigators deem would jeopardize the safety of the potential participant.

We will randomize 200 participants to the Choice group and 200 to the No Choice group. Those in the Choice group will choose which exercise program to undertake – GEMS-T or GEMS-S. In the No Choice group, we will randomize 100 participants to GEMS-S and 100 to GEMS-T (see Figure 1). Four sites (Shepherd Center with help from UGA, Marquette University, Cleveland Clinic, and University of Colorado) will each recruit 80 participants. UNC and MGH will together recruit a total of 40 participants. UAB will recruit at least 40 participants with help from the Tanner Center, a Birmingham-based multidisciplinary center providing neurology, nursing, infusion, clinical research, neurodiagnostic testing, occupational therapy, physical therapy, speech/language pathology, licensed professional counseling, group wellness classes, and individual personal training in one central location.

[figure not shown]

Figure 1: Randomization Scheme for Each Participant

Recruitment methods

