Lost to Contact

If a participant is lost to contact for 2 weeks, the research coordinator will try to contact them via all modes of communication, including personal phone, emergency contact, text, email, and postal service.

If the participant is lost for an additional 2 weeks (a total of 4 weeks), then they will be considered lost and dropped from the study.

If a participant is randomized to a treatment group but makes no contact in the first week, they will be dropped from the study.

If a participant withdraws or is dropped from the study, the research coordinator documents the date and reason in the Portal. This information will be summarized annually for the site-specific IRBs as well as for the Shepherd (Primary site) IRB, the Advisory Board, and the Data Safety Monitoring Board (DSMB), and will be reported in the Final Project report. We will not automatically replace withdrawals, but will develop a strategy based on the attrition rate after the first few waves have completed the study.

Other Withdrawals

To assist with the study intent to treat analyses, the study will attempt to collect data from withdrawals. Research Coordinators will offer participants who withdraw three options:

- 1) Early Termination Visit: Participants will return to the facility to complete a full set of CRO and PRO assessments (including the feedback survey) and subsequently their withdrawal will be processed. Participants receive the \$25 travel stipend for the visit.
- 2) Continue with assessments only: Participants will cease the exercise program but continue with assessments on schedule and per protocol.
- 3) Complete an immediate withdrawal: Participants withdraw immediately and fully from both the exercise program and assessments.

Should a participant choose 1) or 2), they will sign a new consent form with information about participating in these withdrawal assessments (ICF Withdrawal – Early Termination Visit or ICF Withdrawal – Assessments Only).

INTERVENTION

There are two modes of delivering the evidence-based, individualized exercise program: Facility-based exercise training (GEMS-S) and Telerehab-based exercise training (GEMS-T). GEMS-S will be delivered at each of the eight recruiting sites (n=200) and GEMS-T will be delivered via UAB within a participant's home/community (n=200). Both GEMS-S and GEMS-T consist of an identical, individualized exercise program based on evidence-based exercise guidelines.

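### SA2: the Choice-by-treatment interaction does not show whether the effect of choice is the same in both delivery modes, because Choice participants select their own mode

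*SAP*

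**What the plan says.** The protocol (Participants) sets out two stages. First, "We will randomize 200 participants to the Choice group and 200 to the No Choice group". Then, "In the No Choice group, we will randomize 100 participants to GEMS-S and 100 to GEMS-T", while "Those in the Choice group will choose which exercise program to undertake – GEMS-T or GEMS-S". The Intervention section plans 200 participants in each mode.

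For the comparison of choice, the protocol's Data analysis plan says "we will use the same analysis model but examine an interaction term for choice and treatment". The SAP (Data analysis plan, SA2; there TET is GEMS-T and FET is GEMS-S) specifies an "interaction term for Choice and treatment and contrasts will be conducted comparing the four cells" and then gives the interpretation: "We will assess if the effect of Choice is the same for both treatments".

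Both documents, in stating SA2, describe the Choice participants as having been randomised to the mode they prefer. That does not agree with the Participants section.

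The primary model, which SA2 reuses, adjusts for age, gender and baseline EDSS (EDSS or PDDS in the protocol), with site as stratification factor. Treatment preference at entry appears once, as a covariate in the SAP's sensitivity analyses. Protocol Tables 1 and 2 list no measure of mode preference, and the Choice form is completed only for people in the Choice arm.

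**The concern.** In a 2x2 factorial trial with both factors randomised, an interaction term does test whether one factor's effect is the same at each level of the other. Here the second factor is not randomised in half of the trial. GEMS-T (Choice) holds only people who prefer GEMS-T, whereas GEMS-T (No Choice) holds everyone's preferences in their natural proportions. The same holds for GEMS-S. Choice v No Choice within a mode is therefore not a comparison of like with like, and the interaction is the difference between two such comparisons.

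The risk runs both ways. If people who prefer telerehabilitation simply tend to change more, or less, on the outcome than people who prefer the facility, the analysis can suggest that choice helps in one mode and not in the other when choice does nothing. A real difference between modes can also be cancelled out. The same contrasts are carried over to MSWS-12, MFIS and NeuroQOL, SA3 uses the same models, and the heterogeneity analyses build on the SA2 model.

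**Working it through.** The documents give no effect size, SD or power calculation for SA2, so there is no planned figure to reproduce. The check concerns what the interaction estimates.

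**Inputs from the documents.** Choice 200; No Choice 100 + 100; 200 planned per mode. The last figure implies 200 - 100 = 100 choosing each mode, so p = 100/200 = 0.5. No choice split is stated outright.

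**Assumptions.** Outcome SD 1; two-sided 5% test; s is the prognostic difference (GEMS-T preferrers minus GEMS-S preferrers) left after covariate adjustment; m is the benefit of receiving the preferred mode, equal in both modes; being offered a choice has no separate effect of its own.

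**Algebra.** Take a common level in each mode, which cancels.

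- GEMS-T (Choice): all prefer GEMS-T, mean s + m. GEMS-T (No Choice): mean p(s + m). So d_T = (1-p)(s + m).
- GEMS-S (Choice): all prefer GEMS-S, mean m. GEMS-S (No Choice): mean ps + (1-p)m. So d_S = p(m - s).
- Interaction = d_T - d_S = s + (1-2p)m.

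At p = 0.5 this is s exactly, whatever m is. At p = 0.7 with s = 0 and m = 0.3 SD it is (1 - 1.4) x 0.3 = -0.12 SD, although choice helps equally in both modes.

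**Rejection rate with no effect of choice (m = 0).** At p = 0.5 the SE is sqrt(4/100) = 0.200. At p = 0.7 the Choice cells are 140 and 60, and the SE is sqrt(1/140 + 1/60 + 2/100) = 0.209. The rate is Phi(s/SE - 1.96) + Phi(-s/SE - 1.96).

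| s (SD) | p = 0.5 | p = 0.7 |
|---|---|---|
| 0 | 5% | 5% |
| 0.1 | 8% | 8% |
| 0.2 | 17% | 16% |
| 0.3 | 32% | 30% |
| 0.5 | 70% | 67% |

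Simulation of 4,000 trials per scenario agrees: at p = 0.5, 31.9% for s = 0.3 and 68.4% for s = 0.5. The unequal split alone (s = 0, m = 0.3, p = 0.7) moves rejection only to about 8-9%.

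**How the contrasts would look.** With s = m = 0.3 and p = 0.5, d_T = 0.5 x 0.6 = 0.30 and d_S = 0.5 x 0 = 0.00. An equal benefit appears to exist in GEMS-T only. Conversely, with benefits m_T = 0.5 and m_S = 0 and s = -0.25, d_T = 0.5 x 0.25 = 0.125 and d_S = 0.5 x 0.25 = 0.125. The interaction is 0 and a real difference is hidden.

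**The randomised comparison.** At p = 0.5, overall Choice minus No Choice is (d_T + d_S)/2 = m/2; s cancels.

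**The case against.** *The SAP already plans to adjust for treatment preference at entry.* This is the best reply. In simulation at 50:50, adding preference for all 400 participants brought rejection under pure selection back to about 5% (5.3% at s = 0.25 SD, 4.9% at 0.50 SD). But the adjustment is only a sensitivity analysis, and no listed instrument records preference in No Choice participants. In the Choice arm, preference and mode received coincide. A preference main effect also leaves the -0.12 SD in place at p = 0.7 and m = 0.3.

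*The covariates handle selection.* Age, gender, EDSS and site remove only the part of s that they explain.

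*The size of s is unknown.* This stands. If s = 0 and the split is 50:50 with equal benefits, the test keeps its 5% level, and at 0.1 to 0.2 SD the inflation is modest.

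*The design's own estimators do not answer the question either.* This also stands. At 50:50 the selection estimator is 0.5 x (d_T/0.5 - d_S/0.5) = d_T - d_S, the same statistic as the interaction. With unequal benefits it estimates s + (m_T - m_S)/2, which is still a mixture: s = 0, m_T = 0.5 and m_S = 0 give 0.25 SD with no selection at all. The gain is a correct label and a separate estimate of the preference effect, not a test of equality.

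*SA2 is not the primary hypothesis.* True. A reader might take the SAP's statement that the impact of choice is among its primary interests (heterogeneity section) as making this interaction central. That passage concerns the impact of choice on the performance and benefits of exercise and does not rest on this term.

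**Conclusion.** The stated interpretation is wrong as written and should be corrected. Under equal matching benefits the interaction estimates s + (1-2p)m, which is the prognostic difference between the two kinds of chooser at the implied 50:50 split. The within-mode Choice v No Choice contrasts have the same defect. The algebra follows from the allocation scheme. The rejection rates (about 8% to 70% for s of 0.1 to 0.5 SD) depend on an s that the documents do not give, on SD 1, and on 100 per cell.

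Two stronger conclusions might be inferred and are not supported. One is that the trial will report a false difference in the effect of choice between modes: that depends on s, which may be small. The other is that the trial cannot study choice: overall Choice v No Choice, and GEMS-T v GEMS-S within No Choice, are randomised comparisons and are untouched.

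**What to change.** In the SAP, with matching text in the protocol:

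1. Delete the sentence that reads the interaction as equality of the choice effect, and correct the SA2 description of Choice participants as randomised to their preferred mode.
2. Make overall Choice v No Choice, by first-stage arm, the main test of choice. Estimate the treatment effect within No Choice.
3. Pre-specify the two-stage choice-design decomposition. With p-hat the share of the Choice arm choosing GEMS-T:
   - preference effect = 0.5 x [d_T/(1 - p-hat) + d_S/p-hat]
   - selection effect = 0.5 x [d_T/(1 - p-hat) - d_S/p-hat]

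   Use cell means adjusted for site, age, gender and EDSS, within the imputation procedure. Take intervals from a bootstrap within randomised arm, so that uncertainty in p-hat is included.
4. State the assumptions: an equal matching benefit in both modes, and no separate effect of being offered the choice. State also that mode-specific choice effects cannot be separated from selection unless preference is recorded in everyone.
5. Apply the same caution to the within-mode contrasts for adherence, dropout, MSWS-12, MFIS, NeuroQOL and SA3.

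The cost is SAP wording and a short program; no new data are needed. At s = m = 0.3 and p = 0.5, simulated estimates averaged 0.30 for both effects, with an SE of about 0.21. The downsides are wider intervals when the split is uneven (for the selection effect at 70:30, an SE of about 0.25 against 0.21 for the interaction) and giving up any claim that choice works differently by mode.
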